9.4 Data management and quality control

For studies using eCRFs, Novartis personnel (or designated CRO) will review the data entered by investigational staff for completeness and accuracy. Electronic data queries stating the nature of the problem and requesting clarification will be created for discrepancies and missing values and sent to the investigational site via the EDC system. Designated investigator site staffs are required to respond promptly to queries and to make any necessary changes to the data.

Concomitant treatments and prior medications entered into the database will be coded using the WHO Drug Reference List, which employs the Anatomical Therapeutic Chemical classification system. Medical history/current medical conditions and adverse events will be coded using the Medical dictionary for regulatory activities terminology.

The occurrence of any protocol violations will be determined. After these actions have been completed and the data has been verified to be complete and accurate, the database will be declared locked. Authorization is required prior to making any database changes to locked data, by joint written agreement between the Global Head of Biostatistics and Data Management and the Global Head of Clinical Development.

For EDC studies, after database lock, the investigator will receive a CD-ROM or paper copies of the patient data for archiving at the investigational site.

10 Statistical methods and data analysis

Novartis or a designated Contract Research Organization will perform all analyses. Any data analysis carried out independently by the investigator should not be presented or published before the final analysis is completed. The data from all centers that participate will be combined in the analyses.

Final analyses will be performed when all patients have been followed for 30 days after they have either prematurely discontinued or been discontinued from the study after completing treatment as per protocol.

Data will be summarized with respect to demographic and baseline characteristics including FLT3 (ITD&TKD) and NPM1 mutation (when available), and safety and efficacy observations and measurements. Data may be summarized by different chemotherapy regimens (i.e. the “7+3” and the “5+2” induction regimens) and treatment phases (induction, consolidation and maintenance).

Categorical data will be presented as frequencies and percentages. For continuous data, mean, standard deviation, median, minimum, and maximum will be presented. For selected parameters, 25th and 75th percentiles will also be presented.

10.1 Analysis sets

The following analysis sets will be used for statistical analysis and data reporting.

The ‘All enrolled patients’ set comprises all screened patients who are not screening failures.

10.1.1 Full Analysis Set

The Full Analysis Set (FAS) comprises all patients who received at least one dose of midostaurin and have a documented FLT3 mutation (ITD or TKD).

10.1.2 Safety set

The Safety Set comprises all patients who received at least one dose of midostaurin.

10.1.3 Per-Protocol set

Not applicable

10.1.4 Dose-determining analysis set

Not applicable

10.1.5 Pharmacokinetic analysis set

Not Applicable

10.1.6 Other analysis sets

Not Applicable

10.1.6.1 Efficacy/evaluable set

Not Applicable

10.2 Patient demographics/other baseline characteristics

Demographic and other baseline data will be summarized descriptively for the safety set.

Relevant medical histories and current medical at baseline will be summarized by system organ class and preferred term for all patients.

10.3 Treatments (study treatment, concomitant therapies, compliance)

The safety set will be used for the analyses below. Categorical data will be summarized as frequencies and percentages. For continuous data, mean, standard deviation, median, 25th and 75th percentiles, minimum, and maximum will be presented.

Duration of midostaurin treatment exposure in days and cumulative dose and dose intensity will be summarized overall and by period and induction chemotherapy regimen by means of descriptive statistics using the safety set.

The number of patients with dose adjustments (reductions, interruption, or permanent discontinuation) and the reasons will be summarized for all patients and all dosing data will be listed.

Concomitant medications and significant non-drug therapies prior to and after the start of the study treatment will be listed and summarized according to the Anatomical Therapeutic Chemical (ATC) classification system, for all patients.

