6.3.2.4 Other non-hematologic toxicities

If a patient experiences other grade 3/4 non-hematologic toxicity, which is considered to be at least possibly related to midostaurin, midostaurin must be interrupted until toxicity resolves to \leq grade 1. Missed doses of midostaurin will not be made up.

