### **Date of last administration of study drug**

The date of last administration of study drug is defined as the last date when a nonzero dose of study drug is administered. This date is also referred to as **last date of study drug**. Last date of study drug is defined for each drug which is part of study treatment, by period (induction, consolidation, maintenance, where applicable) and overall.

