#### **Study treatment and Midostaurin**

The duration of exposure for the **study treatment and Midostaurin** will be calculated by cycle, period (induction, consolidation, maintenance) and overall as:

- Duration of study treatment/Midostaurin exposure (days) in a **cycle** = [(date of last administration of study treatment/Midostaurin in that cycle) - (date of first administration of study treatment/Midostaurin in that cycle) + 1]
- Duration of study treatment exposure (days) in a **period** = sum of durations of study trt/Mido exposure (days) in each cycle of that period.
- **Overall** duration of study treatment exposure (days) = [(date of last administration of study treatment/Midostaurin) - (date of first administration of study treatment/Midostaurin) + 1]
- If the start or end date of a study drug is missing, the duration will be missing. The durations will include periods of temporary interruption (planned or actual) for any reason.

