### **Actual dose intensity (DI)**

Dose intensity (DI) will be derived for each of the study drugs: midostaurin, daunorubicin and idarubicin.

DI for patients with non-zero duration of exposure is defined as follows:

$DI \text{ (dosing unit / unit of time)} = \text{Actual cumulative dose (dosing unit)} / \text{Duration of exposure (unit of time)}$ .

For example, DI (mg/day) = Actual cumulative dose (mg) / Duration of exposure (day)  
= 1300 mg / 14 days  
= 92.9 mg/day

For patients who did not take any study drug the DI is by definition equal to zero.

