## 2.5.2 Study treatment and tolerability

### Study treatment

Duration of exposure (days), actual cumulative dose and actual dose intensity will be summarized by period and overall for each of the study drugs: midostaurin, daunorubicin and idarubicin for the safety set. Duration of exposure (days), actual cumulative dose and actual dose intensity will be summarized also by cycle. The number of patients with midostaurin dose changes, interruptions and permanent discontinuations will be presented by age category and overall, along with reasons for the dose change/interruption/permanent discontinuation.

Duration of midostaurin treatment exposure (days) will also be categorized and summarized by period and overall for the safety set using the following intervals:

- ≤ 20; >20; >40; >60; >120; >180; >240; >300; >360

Duration of study treatment exposure (days) will be summarized by period and overall for the safety set using the following intervals:

- ≤ 28; >28; >56; >84; >112; >196; >280; >364; >448; >532

Duration include the rest/recovery days between cycles and will be derived as the following:

Last intake of any study treatment component – first intake of any study treatment component +1

If there are more than 10 patients in each regimen exposure will be further summarized by regimen (“7+3” and “5+2”).

Data will be listed for all patients in the safety set.

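### By cycle and by period, midostaurin dose intensity ignores undosed days at either end of a cycle, so a cycle stopped early at full dose still scores 100 mg/day

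*Protocol*

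**What the plan says.** Protocol 10.3 names the output but gives no formula: "Duration of midostaurin treatment exposure in days and cumulative dose and dose intensity will be summarized overall and by period and induction chemotherapy regimen". SAP 2.5.2 extends it: "Duration of exposure (days), actual cumulative dose and actual dose intensity will be summarized also by cycle".

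The definitions are in SAP 2.1.1:

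- **Ratio:** "DI (mg/day) = Actual cumulative dose (mg) / Duration of exposure (day".
- **Numerator:** the sum of the non-zero doses recorded.
- **Denominator for a cycle:** "date of last administration of study treatment/Midostaurin in that cycle) - (date of first administration of study treatment/Midostaurin in that cycle) + 1".
- **Denominator for a period:** the cycle durations added up.
- **Last administration:** "the last date when a nonzero dose of study drug is administered". The SAP states this by period and overall; I apply the same meaning within a cycle.
- **Interruptions:** temporary interruptions are included in duration, which in practice means those between the first and last dose.

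Neither document defines a dose intensity relative to the scheduled dose.

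**The concern.** A dose-intensity figure is normally read as how much of the intended drug patients received per unit of time. Here the observation window closes at the last dose actually taken in the cycle. If toxicity ends dosing on Day 14 and nothing more is taken before Day 28, the 14 lost days disappear from the calculation and the cycle looks fully dosed.

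The pattern is foreseeable. For related grade 3/4 non-hematologic toxicity in induction and consolidation, Protocol 6.3.2.4 interrupts midostaurin until resolution and adds: "Missed doses of midostaurin will not be made up". Dosing in those cycles ends at Day 28, so a hold that starts late enough, or a permanent stop, produces a truncated cycle.

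What is at stake is the comparison of intensity between cycles, phases and induction regimens. For truncated cycles the ratio is pulled towards the prescribed 100 mg/day, and it can place a patient who missed two weeks above one who missed three days.

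**Working it through.** **Plan's own figure.** SAP 2.1.1 works an example, "1300 mg / 14 days", and reports 92.9 mg/day. 1300/14 = 92.86, so it is reproduced.

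**Inputs.** From Protocol Tables 6-1 to 6-3, midostaurin is 50 mg twice daily, which is 100 mg/day.
- Induction or consolidation cycle: Days 8-28, 21 dosing days, 2100 mg.
- Maintenance cycle: Days 1-28, 28 dosing days, 2800 mg.

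**Formulas.**
- SAP dose intensity = cumulative dose / (last dose day − first dose day + 1), with durations summed over cycles for a period.
- Share of schedule = cumulative dose / scheduled dose.

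**One induction or consolidation cycle, full daily dose on every dosed day**

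| Pattern | SAP dose intensity (mg/day) | Share of schedule |
|---|---|---|
| Days 8-28 complete | 2100/21 = 100.0 | 100% |
| Stopped after Day 14 | 700/7 = 100.0 | 700/2100 = 33% |
| Stopped after Day 8 | 100/1 = 100.0 | 100/2100 = 4.8% |
| First dose delayed to Day 15 | 1400/14 = 100.0 | 1400/2100 = 67% |
| 3-day pause, Days 15-17, resumed | 1800/21 = 85.7 | 1800/2100 = 86% |
| 10-day hold, Days 12-21, resumed | 1100/21 = 52.4 | 1100/2100 = 52% |
| 14-day hold, Days 10-23, resumed | 700/21 = 33.3 | 700/2100 = 33% |

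The ratio tracks the share of schedule when dosing resumes in the cycle. It fails when the missed days lie at either end.

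**How easily a hold reaches the cycle end.** With start days 9 to 28 (20 possibilities), a hold of 14 days runs to Day 28 or beyond for 14 of them, and a hold of 20 days for all 20. This counts calendar possibilities; it is not an estimate of frequency.

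**Period of two such cycles**
- One full, one stopped after Day 14: 2800/28 = 100.0 mg/day, with 2800/4200 = 66.7% of schedule.
- One full, one with a 3-day pause: 3900/42 = 92.9 mg/day, with 92.9% of schedule.

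**Two maintenance cycles.** I assume a hold does not move the cycle boundaries; Protocol 7.1 keeps visits on the cycle-day calendar.
- 28-day hold, cycle 1 Day 15 to cycle 2 Day 14 (28 days is the longest drug holiday in Protocol 6.3.3.4): 2800/28 = 100.0 mg/day, with 2800/5600 = 50% of schedule.
- 3-day pause: 5300/56 = 94.6 mg/day, with 94.6% of schedule.

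**Overall figure, for contrast.** Its denominator is last minus first dose over the whole study, plus 1. For two induction cycles with 3 recovery days:
- Full: 4200/(21+3+7+21) = 4200/52 = 80.8.
- 3-day pause in cycle 2: 3900/52 = 75.0.
- Stopped after Day 14 of cycle 2: 2800/(21+3+7+7) = 2800/38 = 73.7.

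The order is not reversed here.

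**Group size of the effect, by assumption only.** If a fraction p of induction or consolidation cycles lose their last m days and the rest are complete, the mean SAP value stays at 100 mg/day while the mean share of schedule is 100 × (1 − p × m/21)%.
- p = 0.2: m = 7 gives 93%; m = 14 gives 87%.
- p from 0.1 to 0.4: 97% (p = 0.1, m = 7) down to 73% (p = 0.4, m = 14).

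**The case against.** The strongest reply is that the lost dosing is already visible. SAP 2.5.2 reports duration and cumulative dose by cycle, by period and overall, and by regimen if each has more than 10 patients. Because the prescribed dose is fixed, a cycle stopped after Day 14 shows as 7 days and 700 mg. Interruptions and permanent discontinuations are tabulated with reasons and by age. A hold that spans two cycles still lies between two non-zero records and so counts as an interruption. This largely stands, and it limits the impact. It does not remove the point: the interruption and discontinuation tables count patients and reasons rather than dose lost, and cumulative dose by period mixes lost days with the number of cycles given, which varies by design.

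A reader might infer four stronger things that the documents do not support:

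- *Any long hold outranks a brief pause.* It does so only if it runs to the cycle end or delays a first dose. Resumed within the cycle, a 14-day hold scores 33.3 against 85.7.
- *The primary safety result is affected.* The primary endpoint is the proportion of patients with adverse events, grade 3 and 4 events, serious events, events leading to discontinuation, and deaths. Tolerability is defined through reductions and interruptions due to adverse events. Dose intensity enters neither, nor any adverse-event rate.
- *Truncated cycles are the usual course.* The dosing rules make them possible; no frequency is given.
- *A shortfall between groups would be hidden.* It is hidden in this ratio, not in the duration and cumulative-dose tables.

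There is also a fair objection to the obvious remedy. Charging a full schedule to every cycle started penalises stops for relapse, death, transplant or withdrawal, which are not tolerability. The fix has to allow for that.

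**Conclusion.** The point holds for midostaurin dose intensity by cycle and by period. The rule is explicit and gives a misleading value for truncated or late-started cycles: 100 mg/day at full prescribed dose however few days were taken. In the example, 33% of schedule scores 100 mg/day and 86% scores 85.7. Dose reductions, and pauses resumed within the cycle, do lower the ratio. The overall figure is outside this point.

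The consequence is a misleading descriptive exposure summary, partly offset by the neighbouring tables. It is worth correcting but does not threaten the trial's main conclusions.

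Assumptions: midostaurin durations use midostaurin dates; the non-zero rule applies within a cycle; cycle boundaries do not shift during a hold (needed only for the maintenance example). Variable derivations are in a separate programming specification that is not available here and could differ. SAP 2.5.2 also says that study-treatment duration by period includes recovery days, whereas SAP 2.1.1 sums cycle durations; these two should be reconciled.

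**What to change.** In SAP 2.1.1 and 2.5.2:

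1. Keep the by-cycle and by-period ratio, but label it *intensity while dosing*.
2. Beside it, add relative dose intensity for midostaurin = actual cumulative dose / scheduled cumulative dose. The denominator is the protocol's own schedule: 21 dosing days for each induction or consolidation cycle started and 28 for each maintenance cycle started, at 100 mg/day. Report it by cycle, period and regimen.
3. Show it with and without cycles ended by relapse, death, transplant or consent withdrawal, so that disease course is not read as poor tolerability.

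The cost is one derived variable from dosing records already collected, plus a flag for the reason a cycle ended. Reported intensity will look lower. The SAP's latest update postdates database lock, so the addition should be labelled post hoc. No treatment rule changes.

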10.4 Primary objective

The primary objective is to further assess the safety of midostaurin in induction, consolidation and maintenance therapy including the '7+3' regimen, daunorubicin (60-90mg/m²/day), the substitution of daunorubicin by idarubicin (12 mg/m²/day) and cytarabine (100-200 mg/m²/day) and also allowing the "5+2" reduced dose regimen.

The safety set will be used for the analysis of clinical safety data.

10.4.1 Variable

The analysis of the primary objective is described in [Section 10.5.3](#).

10.4.2 Statistical hypothesis, model, and method of analysis

No statistical hypotheses are being tested in this study.

10.4.3 Handling of missing values/censoring/discontinuations

No imputation will be applied for any missing data.

10.4.4 Supportive and sensitivity analyses

Not Applicable

10.5 Secondary objectives

The secondary objectives in this study are to assess the clinical efficacy of midostaurin in sequential combination with chemotherapy regimens in induction and consolidation and the clinical efficacy of midostaurin in maintenance phase (measured by CR/CRI rate).

Clinical efficacy rate is defined as the proportion of patients with complete remission (CR) or complete remission with incomplete hematologic recovery (CRI) as per local assessment, in induction, consolidation and maintenance. CR and CRI are defined according to the Revised Recommendations of the International Working Group for Diagnosis, Standardization of Response Criteria, Treatment Outcomes, and Reporting Standards for Therapeutic Trials in Acute Myeloid Leukemia, described in the ELN recommendations 2017 ([Dohner et al 2016](#)) (ENL).

Clinical efficacy rate will be calculated based on the FAS. Clinical efficacy rate and its 95% confidence interval will be presented by induction regimen and age category as described in [Section 10.5.3.1](#).

10.5.1 Key secondary objective(s)

Not Applicable

10.5.2 Other secondary efficacy objectives

Not Applicable

10.5.3 Safety objectives

10.5.3.1 Analysis set and grouping for the analyses

For all safety analyses, the safety set will be used.

The overall observation period may be summarized into the following mutually exclusive periods:

1. **Pre-treatment period:** prior to first dose of midostaurin
2. **On-treatment period** (includes 3 mutually exclusive periods):
 - a. Induction period: From day of first dose of midostaurin to the day before start of consolidation period (i.e. end of induction phase plus any rest/recovery days)

- b. Consolidation period: From day of first dose of study treatment in consolidation phase to the day before start of maintenance (i.e. end of consolidation phase plus any rest/recovery days)
- c. Maintenance period: From day of first dose of midostaurin in the maintenance phase to the date of last dose of midostaurin + 30 days

It is noted that if a patient permanently discontinues study treatment during any of these periods, on-treatment is considered until the date of last dose of study treatment + 30 days (unless patient died before then, then it is till the death date)

3. **Post-treatment period:** from last date of study treatment + 31 days to end of study

Each period will contain all patients who entered that period (including withdrawal, drop-outs etc.).

Data may also be summarized by different chemotherapy regimens (i.e. the “7+3” and the “5+2” induction regimens) and by age category (i.e. patients younger than 60 years old and patients 60 years old or older).

10.5.3.2 Adverse events (AEs)

Summary tables for adverse events (AEs) will include only AEs that started or worsened during the on-treatment period, the **treatment-emergent** AEs.

The incidence of treatment-emergent adverse events (new or worsening from baseline) will be summarized by system organ class, preferred term, severity (based on CTCAE grades), type of AE, relation to study treatment, periods and regimens as specified above and overall. AEs with different starts dates in different periods will be counted within each period.

AEs leading to discontinuation, serious AEs (SAE) and non-SAEs during the on-treatment period will be tabulated by type of AE.

All deaths (on-treatment and post-treatment) reportable as SAEs and non-fatal SAEs will be listed by patient and tabulated by type of AE.

All AEs, deaths and SAEs (including those from the pre and post-treatment periods) will be listed and those collected during the pre-treatment and post-treatment period will be flagged.

10.5.3.3 Laboratory abnormalities

Not Applicable

10.5.3.4 Other safety data

Other safety data (including vital signs and weight) will be summarized and listed, notable values will be flagged, and any other information collected will be listed as appropriate.

ECG

A standard 12-lead ECGs including PR, QRS, QT and QTcF intervals will be obtained for each subject during the study. ECG data will be read and interpreted locally.

Listing will be provided with notable values flagged.

Vital signs

Data on vital signs will be tabulated and listed, notable values will be flagged.

10.5.3.5 Supportive analyses for secondary objectives

Not Applicable

10.5.3.6 Tolerability

Tolerability will be studied in terms of dose reductions or dose interruption due to an AE. Number and percentage of patients who have a dose modification due to a treatment related adverse event will be summarized by type of dose modification (interruption, dose reduction, and permanent discontinuation).

10.5.4 Pharmacokinetics

Not Applicable

10.5.4.1 Data handling principles

Not Applicable

10.5.5 Biomarkers

Not Applicable

10.5.6 Resource utilization

See [Section 10.6](#).

[REDACTED]

10.6 Exploratory objectives

[REDACTED]

[REDACTED]

10.6.2 Resource utilization

Similarly descriptive statistics will be applied to assess resource utilization, e.g. on the reason for hospitalization, number of hospital days by ward type, discharge reason, and the concomitant medications used during hospital stay.

10.7 Interim analysis

No formal interim analysis is planned for this study. Analyses may be performed periodically (e.g. annually), if needed, to fulfill regulatory requests, safety updates or for publication purposes.

10.7.1 Progression free survival (PFS)

Not Applicable

10.7.2 Key secondary endpoint: Overall survival (OS)

Not Applicable

10.8 Sample size calculation

Approximately 300 patients will be enrolled in this study. The planned sample size is based on the average expected accrual rate (17 patients per month) and the planned recruitment duration (18 months) of the trial. The actual sample size may differ from this planned number. A sample size of 300 patients provides a 95% probability of observing at least one patient with an adverse event (AE) assuming a true probability of occurrence of 1%.

[Table 10-1](#) provides probabilities to detect at least one patient with an AE for different sample sizes and different true AE incidences.

Table 10-1 Probability to detect at least one patient with an AE for different sample sizes and different true AE incidences

Incidence of an adverse event	Sample size		
	N=200	N=250	N=300
0.4%	0.5514	0.6329	0.6995
0.5%	0.6330	0.7144	0.7777
0.6%	0.6999	0.7779	0.8356
0.8%	0.7994	0.8657	0.9102
1.0 %	0.8660	0.9189	0.9510
1.3%	0.9270	0.9620	0.9803

